8.6.1.2. Assessment of Adverse Events

Investigators will seek information on AEs at each subject contact. Subjects should be asked using a general, non-direct question if there has been any change in their general health. Direct questioning and examination should then be performed as appropriate.

Severity of the AE should be assessed according to the following criteria:

Mild: No interference with the subject's daily activities; no medical intervention/therapy required.

Moderate: Possible interference with the subject's daily activities; no or minimal medical intervention/therapy required.

Severe: Considerable interference with the subject's daily activities; medical intervention/therapy required.

Regardless of severity, some events may also meet regulatory serious criteria. Refer to definitions and reporting of serious adverse events (SAEs) in [Section 12.4](#), Appendix D.

An Investigator who is medically qualified must make the determination of relationship (related or not related) to the investigational product for each AE or SAE. When determining relationship to study medication, the Investigator will consider any investigational products that a subject could be exposed to in this clinical trial. The Investigator should decide whether there is a reasonable possibility that the study medication caused the event, taking into account the following: a) evidence, b) science-based rationale, c) medical and clinical judgment, d) mechanisms of action, e) biologic plausibility, f) confounding risk factors (i.e., medical history, concomitant medications), g) temporal relationship, h) dechallenge/rechallenge, and i) lack of alternative explanation.

- The event may be recorded as Related to investigational product or
- Reporting the event as Not Related to study medication be considered

8.6.1.3. Reporting Adverse Events

AEs, whether spontaneously reported by the subject or noted by authorized study personnel, will be recorded in the subject's medical record and on the appropriate AE eCRF. Each recorded AE will be described by its duration (represented in dates), affected eye(s) (if applicable), maximum severity of the AE, seriousness criteria, suspected relationship to the study medication, actions taken with the study medication, and the study participation, outcome of the AE, and any other attributable causes of the AE.

Regardless of relationship to the clinical study, AEs that occur at any time after the subject has provided written informed consent until subject withdrawal or the scheduled exit visit, must be recorded. To improve the quality and precision of acquired AE data, Investigators should observe the following guidelines:

- Whenever possible, use recognized medical terms when recording. Do not use colloquialisms and/or abbreviations.
- If known, record the diagnosis (i.e., disease or syndrome) rather than component signs and symptoms and /or laboratory or test findings (e.g., record congestive heart

failure rather than dyspnea, rales, and cyanosis, and enlarged heart on chest x-ray). However, other events that are considered unrelated to an encountered syndrome or disease should be recorded as individual AEs (e.g., if congestive heart failure and severe headache are observed at the same time and are clinically unrelated, each event should be recorded as an individual AE).

- If the diagnosis is not known, then record the leading component sign, symptom, or test finding and describe the other clinically related findings in the narrative description of the case. A suspected diagnosis can be used and described as such (e.g., record suspected or probable myocardial infarction); this has to be updated in the clinical database once the diagnosis is confirmed.

AEs occurring secondary to other events (e.g., sequelae) should be identified by the primary cause. A primary AE, if clearly identifiable, generally represents the most accurate clinical term. If a primary AE is recorded, events occurring secondary to the primary event should be described in the narrative description of the case. For example:

The subject developed orthostatic hypotension and subsequently fainted and fell to the floor wherein she experienced a head trauma and neck pain.

The primary AE in this example is orthostatic hypotension. The fall, head trauma, and neck pain should be described in the narrative description of the case.

- For intermittent events (e.g., intermittent headache), the event onset date should be recorded as the date the subject first started to experience the event and resolution date should reflect when the last occurrence resolved or stopped. Separate AEs for each event should not be recorded. For example, if a subject experienced headache on 14SEP2015 lasting for three hours, then subsequently experienced intermittent episodes of headache every day for approximately 3 hours until 21SEP2015, then the AE date of onset is 14SEP2015 and the resolution date is 21SEP2015.
- For intermittent events, record the maximum severity of the individual events. For example, if a subject complains of intermittent headaches for one week and the severity of each headache ranges from mild to moderate, then the severity would be moderate.
- For intermittent hospitalizations occurring for a primary AE (e.g., in a subject with multiple sclerosis, commonly known for its relapsing and remitting course, in some cases leading to multiple hospital confinements), the subsequent hospitalizations should be described in the narrative description of the case.
- If treatment was initiated, include the treatment and duration of the medication(s) in the eCRF.

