8.6.2.2. Reporting Serious Adverse Events

The SAE eCRF must be completed with as much information as is available within 24 hours of knowledge of the event.

To improve the quality and precision of acquired SAE data, Investigators should observe the following guidelines:

- Death: Death is an outcome of an event. The event that resulted in the death should be recorded and reported as the SAE.
- Hospitalizations for Surgical or Diagnostic Procedures: The illness leading to the surgical or diagnostic procedure should be recorded as the SAE, not the procedure itself. The procedure should be captured in the case narrative as part of the action taken in response to the illness.

Depending on the nature and seriousness of the AE, Santen may request additional documentation, for example, copies of the ophthalmic and medical records as well as results of laboratory tests. If the subject was hospitalized, a copy of the discharge summary may be requested.

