A SAE is defined as any untoward medical occurrence that, at any dose:

 a. Results in death

 b. Is life-threatening

The term 'life-threatening' in the definition of 'serious' refers to an event in which the participant was at risk of death at the time of the event. It does not refer to an event, which hypothetically might have caused death if it were more severe.

 c. Requires inpatient hospitalization or prolongation of existing hospitalization 
In general, hospitalization signifies that the participant has been detained (usually involving at least an overnight stay) at the hospital or emergency ward for observation and/or treatment that would not have been appropriate in the physician's office or outpatient setting. Complications that occur during hospitalization are AEs. If a complication prolongs hospitalization or fulfills any other serious criteria, the event is serious. When in doubt as to whether "hospitalization" occurred or was necessary, the AE should be considered serious.
 
Hospitalization for elective treatment of a pre-existing condition that did not worsen from baseline is not considered an AE.

 d. Results in persistent disability/incapacity 
 • The term disability means a substantial disruption of a person's ability to conduct normal life functions. • This definition is not intended to include experiences of relatively minor medical significance such as uncomplicated headache, nausea, vomiting, diarrhea, influenza, and accidental trauma (e.g., sprained ankle) which may interfere with or prevent everyday life functions but do not constitute a substantial disruption.

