9.1. Adverse Event

Subjects with any AEs will be tabulated AEs by treatment arm using actual treatment received. Subjects with any AEs will be tabulated by SOC and PT where a subject who experienced multiple AEs within a SOC or PT will be counted only once for that SOC or PT. SAEs, SARs, and Serious SARs will be tabulated similarly.

Subjects with any ocular and non-ocular AEs will be tabulated separately. AEs, ocular, and non-ocular will also be summarized by relationship to treatment and maximum severity. Any ocular AE that occurred simultaneously to both eyes will be counted once.

AE, SARs, ocular and non-ocular AEs will also be summarized by country.

AEs, AEs leading to death, AEs leading to discontinuation, SAEs, and ESIs, if any, will be listed separately.

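### Protocol 8.6.1.3 leaves a secondary event that is itself serious or sight-threatening in the narrative, with no coded term of its own, which conflicts with Appendix D

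*Protocol*

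**What the plan says.** Protocol Section 8.6.1.3 sets the recording rule in three steps. First: "AEs occurring secondary to other events (e.g., sequelae) should be identified by the primary cause". Then a reason: "A primary AE, if clearly identifiable, generally represents the most accurate clinical term". Then the instruction: "If a primary AE is recorded, events occurring secondary to the primary event should be described in the narrative description of the case". In the worked example a subject has orthostatic hypotension, faints, falls, and has head trauma and neck pain. Hypotension is the recorded AE, and "The fall, head trauma, and neck pain should be described in the narrative description of the case". No exception follows for a secondary event that is serious in its own right.

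The same section lists what each recorded AE carries. The list includes the affected eye, "maximum severity of the AE, seriousness criteria, suspected relationship to the study medication, actions taken with the study medication", and the outcome.

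Two other parts of the protocol bear on such chains:
- Section 8.6.2.2, on deaths: "The event that resulted in the death should be recorded and reported as the SAE".
- Appendix D (Section 12.4), definition of SAE: "Complications that occur during hospitalization are AEs. If a complication prolongs hospitalization or fulfills any other serious criteria, the event is serious". The same definition counts any event that puts vision at immediate risk as an SAE and does not exclude secondary events.

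In the SAP, Section 4.3.1 codes each AE to a system organ class and preferred term, and Section 4.3.1.2 decides ocular status from the eye field of the AE form. Section 9.1 states: "Subjects with any AEs will be tabulated by SOC and PT where a subject who experienced multiple AEs" within one class or term is counted once there. The SAP has no rule for coding narrative text.

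**The concern.** An event described only in a narrative is invisible to tables built from coded AE records. That is harmless for minor sequelae, and it is the point of a primary-cause convention. It is less harmless when the sequela is the clinically important event: a head injury needing admission, or an eye injury after a faint. The safety objective is a comparison of DE-126 with timolol, and the tables that serve it are by preferred term, by seriousness and by ocular versus non-ocular.

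The second worry is consistency. If 8.6.1.3 and Appendix D lead to different records for the same chain of events, the term that reaches the SAE table can vary between sites, of which about 45 are planned.

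**Working it through.** There is no stated figure to reproduce; the check is textual. Take a chain in which event A is the primary AE and event B is secondary to A and itself meets a serious criterion. Compare what the data would hold under each instruction.

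| Attribute | B in the narrative only (8.6.1.3) | B recorded as an AE/SAE (Appendix D) |
|---|---|---|
| SOC and preferred term | None for B; SAP 4.3.1 codes AEs, not narratives | B's own |
| Seriousness, outcome, action taken | Can be entered on A | Entered on B |
| Causality | A's assessment only | B's own |
| Ocular status | A's eye field, which is N/A if A is non-ocular (Appendix E; SAP 4.3.1.2) | B's eye field |
| Term in the SAE table | A's, if A is flagged serious | B's |

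1. **Seriousness and outcome.** Section 8.6.2.1 and SAP 4.3.1.1 make an AE serious when it led to death, hospitalization or disability. A can therefore be flagged serious on account of B. SAP 9.1 tabulates SAEs, and lists SAEs, AEs leading to death and AEs leading to discontinuation. This information is not lost.

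2. **Sight-threatening events.** The protocol defines these by immediate risk to vision as a direct result of the event. If A is non-ocular and B injures the eye, it is open to argument whether A meets that wording, so transfer of this flag is less certain.

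3. **Term, causality and ocular status.** None of these transfers. Appendix D requires a causality assessment for each occurrence of each AE or SAE, but B has no record on which to enter one. Appendix E calls for separate forms only for independent events, so it does not bring B back.

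4. **Complications.** Appendix D says that in-hospital complications are AEs and are serious if they meet any serious criterion. A complication of a recorded primary AE is a secondary event under 8.6.1.3. The two instructions give different records for the same occurrence, which is a direct conflict.

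5. **Deaths.** Section 8.6.2.2 asks for the event that resulted in death. If A leads to B and B is the proximate cause, one site could name A under 8.6.1.3 and another could name B. The term is unclear, but neither reading breaks the rule.

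6. **Size.** The protocol's example names three items for the narrative: the fall, the head trauma and the neck pain. It does not say where the faint goes. With 147 subjects planned per arm, one subject missing from a term changes that term's rate by 1/147 = 0.0068, or 0.68 percentage points. That is the weight of one subject, not an estimate of loss.

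**The case against.** The best case for leaving the text alone has four parts.
- Recording by primary cause is a deliberate and sensible convention that stops one episode from inflating the AE tables.
- The text is guidance: it says what investigators should do, applies where a primary AE is clearly identifiable, and does not forbid a separate record.
- Sections 8.6.1.2, 8.6.5 and 8.6.6 send sites to Appendix D for SAEs, and 8.6.5 requires all SAEs to be recorded and reported.
- The rule applies equally to both masked arms.

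The convention deserves to stay for ordinary sequelae, and the cross-references make the gap smaller than 8.6.1.3 alone suggests. They do not close it. Section 8.6.1.3 itself has no pointer to Appendix D, the softening words concern the choice of the primary term rather than the place of the secondary event, and the example puts head trauma in the narrative without comment.

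Several stronger readings are tempting, but the documents do not support them:
- *Serious or fatal consequences never reach the tables.* They can, through the primary AE (step 1).
- *The death rule is contradicted.* Reporting hypotension as the fatal SAE is compatible with 8.6.2.2 as written. The protocol's example is not fatal.
- *Four of five events in the example are lost.* Only three are assigned to the narrative; counting the faint is an addition.
- *Macular edema after intraocular inflammation would vanish.* Section 2.3 gives these as separate cautions and does not describe one as a sequela of the other, although exclusion criterion 16 lists uveitis among the risk factors for macular edema. Subjects with a history of either are excluded. If the chain did occur, the primary event would still count as ocular, and slit-lamp and BCVA changes are summarized independently of AE coding.
- *The comparison between arms is biased.* Nothing in the documents shows a difference between arms in how often such chains occur.

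**Conclusion.** The concern holds in a narrow form. Section 8.6.1.3 lacks an exception for secondary events that are themselves serious or sight-threatening, and so conflicts with Appendix D on complications and on sight-threatening events. The loss is of the secondary event's own preferred term and causality assessment, and of its ocular classification where the primary AE is non-ocular. With the death rule there is tension, not contradiction.

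The likely effect is small in number and falls on the rare events for which individual terms matter most. Its frequency cannot be estimated from the documents. The conclusion assumes that sites follow 8.6.1.3 as written, and that the eCRF completion guidelines mentioned in Section 10.4.1, which are not among the documents, do not already contain the exception.

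**What to change.** Reconcile 8.6.1.3 with Appendix D by adding a sentence such as: *A secondary event that itself meets a serious criterion, including sight-threatening, or that is the event that resulted in death, is also recorded as its own AE/SAE and linked to the primary AE.* Amend the example to say that the head trauma is recorded separately if it meets such a criterion. State in SAP 9.1 that these linked records are tabulated under their own terms. All other sequelae stay in the narrative.

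A wider exception, covering every severe, ocular or discontinuation-causing sequela, would be a trade-off against the primary-cause convention; the conflict with Appendix D does not require it.

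The cost is protocol and eCRF-guideline wording, a link between AE records, and a few more records. The downside is that a few subjects will appear under two related preferred terms.

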8.6.2. Serious Adverse Events

8.6.2.1. Assessment of Serious Adverse Events

An AE is considered serious if it fulfills one or more of the following criteria:

- Death (i.e., the AE caused or led to death).

- It was life threatening (i.e., immediately life-threatening).
- It required or prolonged inpatient hospitalization.
- It resulted in a persistent or significant disability/incapacity (i.e., the AE resulted in a substantial disruption of the subject's ability to carry out normal life functions).
- It resulted in a congenital anomaly/birth defect in the offspring of a study subject who was exposed to study therapy prior to conception or during pregnancy.
- It is a medically significant event(s), which may include "sight-threatening events" that may not meet any of the above serious criteria but may jeopardize the subject or require medical or surgical intervention to prevent one of the outcomes listed above.
 - Sight threatening event: A sight-threatening event is any event that places the subject at immediate risk of permanently losing vision in either eye as a direct result of the event.

8.6.2.2. Reporting Serious Adverse Events

The SAE eCRF must be completed with as much information as is available within 24 hours of knowledge of the event.

To improve the quality and precision of acquired SAE data, Investigators should observe the following guidelines:

- Death: Death is an outcome of an event. The event that resulted in the death should be recorded and reported as the SAE.
- Hospitalizations for Surgical or Diagnostic Procedures: The illness leading to the surgical or diagnostic procedure should be recorded as the SAE, not the procedure itself. The procedure should be captured in the case narrative as part of the action taken in response to the illness.

Depending on the nature and seriousness of the AE, Santen may request additional documentation, for example, copies of the ophthalmic and medical records as well as results of laboratory tests. If the subject was hospitalized, a copy of the discharge summary may be requested.

8.6.2.3. Expedited Reporting of Serious Adverse Events

Santen (or designee) will provide the Principal Investigator with a reporting cover letter and a masked expedited safety report for expedited reporting of SAEs to the IRB or IEC. The Principal Investigator is responsible for receiving and reviewing expedited safety reports, submitting expedited safety reports to the IRB or IEC, and maintaining copies of expedited safety reports in the study records.

8.6.3. Events of Special Interest

The following are considered Events of Special Interests (ESIs) and should be reported on the appropriate eCRF with as much information as available within 24 hours of knowledge of the event:

- Pregnancy:
 - There are no controlled data with the investigational product in human pregnancy. It is required that females of childbearing potential use effective contraception during the study and recommended for 4 weeks for female subjects of childbearing potential and 12 weeks for male subjects capable of fathering children after the completion of the study. Any pregnancy occurring during study treatment should be reported and the subject will be discontinued from the study. The subject should be followed until the end of pregnancy or until the end of the study, whichever is longer.
- Medication administration errors
 - Study medication administration errors determined to be **significant** by the Investigator will be reported and evaluated as ESIs. Examples of study medication administration errors may include, but are not limited to: incorrect dose of study medication and administration of study medication from an incorrect kit. An AE does not necessarily need to have occurred to count as a study medication administration error. A medication administration error is an unintended failure in the process of treatment with a medicinal product that leads to, or has the potential to lead to harm of the subject.

8.6.4. Pregnancy Testing, Monitoring, and Reporting

8.6.4.1. Pregnancy Testing

If the subject is a female of childbearing potential, urine samples will be collected for pregnancy tests as specified in Schedule of Events and Procedures ([Table 3](#)). Urine samples will be analyzed at the site with results available prior to administration of Study Medication.

8.6.4.2. Pregnancy Monitoring and Reporting Procedures

A urine pregnancy test will be conducted using a commercially available test kit at Visit 1 (Screening), Visit 2 (Baseline, Day 1), Visit 4 (Week 6) and Visit 5 Study Exit/Early Termination for all females of childbearing potential.

Although not considered an AE or SAE, pregnancy is an ESI and requires careful monitoring and follow up. If pregnancy is reported by a study subject (or in the partner of a study subject), the investigator must:

- Inform Santen within 24 hours of learning of the pregnancy.
- If the pregnancy has occurred in a study subject, discontinue further study medication administration and/or withdraw the subject from the study.
- Report pregnancy information on the eCRF following instructions.
- Follow the pregnancy until outcome is known. Santen will request specific follow-up on a case-by-case basis.

Additional details regarding collection, reporting, and follow-up of pregnancy is provided below:

Female subjects who become pregnant: The investigator will collect pregnancy information on any female subject who becomes pregnant while participating in this study. Information will be recorded on the appropriate form and submitted to Santen within 24 hours of learning of a subject's pregnancy. The subject will be followed to determine the outcome of the pregnancy. The investigator will collect follow-up information on the subject and the neonate and the information will be forwarded to Santen. Generally, follow-up will not be required for longer than 6 to 8 weeks beyond the estimated delivery date. Any termination of pregnancy will be reported, regardless of fetal status (presence or absence of anomalies) or indication for the procedure. While pregnancy itself is not considered to be an AE or SAE, any pregnancy complication or elective termination of a pregnancy will be reported as an ESI. Abnormal pregnancy outcomes (e.g., spontaneous abortion, fetal death, stillbirth, congenital anomalies, ectopic pregnancy) are considered SAEs and will be reported as such. Any post-study pregnancy-related SAE considered reasonably related to the study medication by the investigator will be reported to Santen. While the investigator is not obligated to actively seek this information in former study subjects, he or she may learn of an SAE through spontaneous reporting. Any female subject who becomes pregnant while participating in the study will discontinue study medication and be withdrawn from the study.

Male subjects with partners who become pregnant: The investigator will attempt to collect pregnancy information on any male subject's female partner who becomes pregnant while the male subject is in this study. After obtaining the necessary signed informed consent from the pregnant female partner directly, the investigator will record pregnancy information on the appropriate form and submit it to Santen within 24 hours of learning of the partner's pregnancy. The female partner will also be followed to determine the outcome of the pregnancy. Information on the status of the mother and child will be forwarded to Santen. Generally, the follow-up will be no longer than 6 to 8 weeks following the estimated delivery date. Any termination of the pregnancy will be reported regardless of fetal status (presence or absence of anomalies) or indication for the procedure.

